After 8 month assessments in the placebo-controlled phase (including 6 months of language intervention), all subjects will enter the extension and be treated with active drug according to the same schedule as in the placebo-controlled phase. All subjects will be dosed with 25 mg BID of unblinded AFQ056 upon completion of the 8 month visit, followed by 2 months of flexible dose forced-titration to the MTD of the dose levels available in the protocol (dose adjustments to be done as described above for the placebo-controlled period for the flexible dose forced-titration). This will be followed by a period of stable treatment. The length of stable treatment will be dependent upon how long after June 15, 2019 the participant enrolls and what dose of drug they are receiving in the open label treatment period. The total duration of the stable treatment for those enrolled after June 15, 2019 will range from 6 months to no open label extension, depending on the number of months after June 15, 2019 the subject is enrolled into the study.

Some subjects will have an acute dose decrease if they were on 50-100 mg BID of active drug in the initial phase but experience from the PK study suggests that children can come off AFQ without withdrawal symptoms and the dose decrease and titration in the open label extension are unavoidable to maintain the blind of the study through the completion of the placebo-controlled period by the final participant. Subjects will continue the language intervention through the extension phase. The open-label extension will allow all children a period of active drug exposure to make recruitment feasible, despite the long placebo period. It will also allow an assessment of more long term-effects of the language intervention and its impact on the ERP and eye tracking biomarker outcomes and other developmental and behavioral outcomes, will allow examination of the trajectory of the language intervention going from placebo to drug treatment in a blinded setting, and will furthermore allow additional long-term safety data to be collected on a larger cohort of children exposed to AFQ056. A diagram of the study design is provided below in Figure 2.

Figure 2. Effects of AFQ056 on Language Learning in Young Children with Fragile X Syndrome (FXS) – Protocol Design

AFQ056 for Language Learning in Children with FXS

Version v15

Version date 02/03/2021

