There is no maximum score except as artificially constrained by the 22-minute duration of dyadic play session; however, in previous studies with children with autism between the ages of 15 to 25 months the range of the score was 5.55 (SD 6.29) at the preintervention visit and 18.91 (SD 20.50) 9 months later at the post-intervention visit. Similarly, Yoder et al. examined growth over time in weighted communication scores for younger siblings of children with autism. Weighted communication scores ranged from 14.4 (SD 10.2) at the initial visit at 14 months to 22.1 (SD 17.9) at the Time 4 visit at 30 months.

The overall weighted communication score will be recorded centrally in the source documents and in the CRFs. 10% of all sessions will be coded by a second independent, blinded coder to determine inter-rater agreement, with agreement above 90% expected as per previous research.

The Weighted Child Intentional Communication Score should be administered by the same rater (SLP or Psychologist) for a given subject at all applicable visits throughout the trial. If the same rater cannot administer the assessment, the site must contact the Study Team prior to proceeding and/or scheduling.

If the subject uses an augmentative communication device, he/she will be permitted to use it if the device serves as the primary form of communication and a SLP has prescribed it. If the subject brings their augmentative communication device to the visit they will be permitted to use it. The scoring of the WCS has been adapted to allow the inclusion of communication acts generated by the child through the use of an augmentative communication device.

Administration time: 22 minutes with subject.

**Mullen Scales of Early Learning (MSEL)** will be administered to all subjects at Screening, AFQ Baseline, 2, 8, and 16 month visits (visits 1, 3, 5, 9, 14). This assessment can be administered by designated and trained staff (Psychologists, and Speech and Language Pathologists preferred).

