The MSEL includes five subscales: gross motor, fine motor, visual reception, expressive language, and receptive language, and an early learning composite (ELC). The subscales yield alpha coefficients between 0.75 and 0.83. Test-retest values range from 0.76 to 0.96 across ages and scales, and inter-rater reliability from 0.91 to 0.96. The MSEL was standardized for children ages 3 months to 68 months but in addition to standard scores also gives age levels of function.

In this study, raw scores and age equivalent scores will be used. Instead of using the ELC, which is not valid in children over age 68 months and not necessarily accurate in populations with intellectual disability, DQ will be calculated from age equivalent scores. Subjects must have a DQ lower than 75% of their chronological age at Screening to be eligible for the study. The

MSEL has been utilized in studies with young children with FXS for many years to track developmental progress . It can be used in children with FXS over 68 months as long as age equivalent scores are used because most children with FXS have significant developmental delays that result in an age equivalency of less than 68 months even when several years older than 68 months. Test booklets with scores will be maintained with the source documents. Raw and age equivalent subscale scores will be entered in the CRFs.

The MSEL should be administered by the same rater for a given subject at all applicable visits throughout the trial. If the same rater cannot administer the assessment, the site must contact the Study Team prior to proceeding and/or scheduling.

*Administration time:* 60 minutes with subject.

**Preschool Language Scales – 5th Edition – the PLS-5** will be administered to all subjects at Screening, AFQ Baseline, 2, 8, and 16 month and Follow Up visits (visits 1, 3, 5, 9, 14). This assessment can be administered by designated and trained staff (Psychologists and Speech and Language Pathologists preferred). This is a comprehensive developmental language assessment that is normed for use with children from birth to 7 years, 11 months of age.

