### 6.3.13 Questionnaires

#### **MacArthur-Bates Communicative Development Inventory**

The MacArthur-Bates Communicative Development Inventory (Words and Sentences version) will be administered at Screening, AFQ Baseline and 2, 4, 6, 8, 12, 16 month and Follow Up visits (visit 1, 3, 5, 7, 8, 9, 12, 14, and 15) to follow language development. This assessment can be administered by a Coordinator, Psychologist or Speech and Language Pathologist. The assessment consists of two parts: a) Part 1 (Words Children Use) is a 680-word vocabulary checklist in which the parent indicates those vocabulary words the child regularly produces in spoken language; and, b) Part 2 (Sentences and Grammar) assesses several aspects of grammar and word endings. This parent-report measure has been well-validated against direct observation and assessment measures of child language status and growth. Test booklets with scores will be maintained with the source documents. Parents will use the same test protocol at each time point using different color ink to indicate newly acquired words or grammatical constructions. Raw scores for each time point will be computed and recorded in the source documents and entered in the CRFs.

The MacArthur Bates Communicative Development Inventory should be administered by the same rater for a given subject at all applicable visits throughout the trial. The parent/legal guardian completing the assessment with the study staff member should also remain the same at all applicable visits throughout the trial. If the same rater cannot administer the assessment and/or the same parent/legal guardian cannot complete the assessment, the site must contact the Study Team prior to proceeding and/or scheduling.

**Administration time:** Caregiver completes independently at own pace, but typically requires no more than 45 minutes.

**The Vineland Adaptive Behavior Scales, Third Edition (Vineland-3)** will be administered as an interview to a parent/caregiver by trained study staff authorized to perform the interview at Screening, AFQ Baseline and 2, 4, 6, 8, 12, 16 month and Follow Up visits (visit 1, 3, 5, 7, 8, 9, 12, 14, and 15). This assessment can be administered by a Coordinator, Psychologist or Speech and Language Pathologist.

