One of the main advantages of using ERPs to analyze cognitive activity is that they provide a continuous measure of processing between a stimulus and a response, which makes it possible to identify and quantify the response and stages of processing that are affected by a specific experimental manipulation. This is especially useful when studying individuals with FXS because they often have hyper reactive responses to stimuli that are auditory, tactile, visual, and olfactory. Van der Molen et al. showed that the N1 and P2 components of sensory evoked potentials from sixteen males with the FXS full mutation and twenty age-matched controls were significantly enhanced in the FXS patients. By focusing on the changes in the N1, P2, and N2 (relative to the common average reference) components of subject ERP signals, between the first and last 45 stimuli presented, Schneider et al. showed that there was abnormal electrocortical habituation to auditory stimuli in patients with FXS, and this improved at N1 and P2 in individuals with FXS who were given minocycline treatment compared to a control group.

The ERP will be administered in an EEG recording session during a single clinic or research visit for each participant at visits 1, 3, 5, 7, 9, 14, and 15. Dense array electrode recording equipment will be used. Stimuli will be presented on a separate computer using Presentation software by NeuroBehavioral Systems, Inc. Event markers synchronized with stimuli will be conveyed to the EEG system over a parallel digital interface.

If the auditory ERP cannot be administered at the screening visit, sites may administer them at the -2 month visit (v2).

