**Forced Titration Design with Sufficient Time and Flexibility to Optimize Dosing:** Given the flexible dose design, it is important to ensure the study participants are on the MTD when they start the language intervention to ensure it is delivered at the presumed most effective dose. In order to achieve the MTD a dose titration period is thus required before starting the language intervention. In prior FXS studies with flexible dosing, it has been clear that because of the frequent day-to-day behavioral ups and downs in patients with FXS that often overlap with potential drug-induced CNS side effects, it is important to have adequate time at each dose to make decisions about dose escalation, and also sufficient flexibility to allow doses to be moved up or down if it becomes clear with time whether a side effect such as hyperactivity or behavioral activation is actually occurring or not. Also, given week-to-week behavioral variability in FXS it is important to avoid leaving the patient on too low of a dose because the family feels

he or she is having a good week and thus titrating to a suboptimal dose and discovering later that transient behavioral improvement had nothing to do with the dosing. Given these considerations, a forced (mandatory) titration strategy was chosen, such that the dose will be titrated up to the next level if there are no side effects, and a 2-month dose titration period with dose adjustments no more frequently than weekly was chosen to ensure plenty of time for careful assessment of side effects and provide enough flexibility to hold or move up or down on doses if it takes more than a week to ascertain whether a dose is producing side effects.

**Tolerance Issues and Assessment:** Concerns have been raised about whether tolerance occurs in previous trials of targeted treatments in FXS; this concern has been raised with respect to AFQ056 treatment although it has not been substantiated. To evaluate for tolerance effects, most outcome measures will be repeated multiple times during treatment period including assessments during the placebo-controlled period at 2 months, 4 months, and 8 months of drug exposure and subsequently during the open-label extension at 2 months, 4 months, and 8 months. This should allow determination of whether tolerance effects are occurring with respect to cognitive language and biomarker measures.

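### Section 9.3's tolerance claim is broader than the extension schedule: the Mullen, PLS-5, ERP and eye tracking each have one on-drug extension assessment, not three

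*Combined protocol and SAP*

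**What the plan says.** Under Tolerance Issues and Assessment, Section 9.3 says that "most outcome measures will be repeated multiple times during treatment period". It gives the times as 2, 4 and 8 months of exposure in the placebo-controlled period and "subsequently during the open-label extension at 2 months, 4 months, and 8 months". It then concludes: "This should allow determination of whether tolerance effects are occurring with respect to cognitive language and biomarker measures". The Open-Label Extension paragraph of the same section also lists the detection of tolerance through repeated assessment as its fifth reason for having the extension.

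Section 6.3 sets the schedule measure by measure:

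- The Mullen (MSEL) "will be administered to all subjects at Screening, AFQ Baseline, 2, 8, and 16 month visits (visits 1, 3, 5, 9, 14").
- The PLS-5 has the same visit numbers: "2, 8, and 16 month and Follow Up visits (visits 1, 3, 5, 9, 14"). Its text also names the follow-up visit, but gives no visit number for it.
- Auditory ERP is recorded "for each participant at visits 1, 3, 5, 7, 9, 14, and 15", and eye tracking is on the same visits.
- The MacArthur-Bates inventory "will be administered at Screening, AFQ Baseline and 2, 4, 6, 8, 12, 16 month and Follow Up visits", and Vineland-3 is on the same visits.

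Extension dosing begins only after the month-8 assessments: "All subjects will be dosed with 25 mg BID of unblinded AFQ056 upon completion of the 8 month visit" (Section 3). At follow-up (visit 15, month 17) children are off drug (Section 6.2.5).

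**The concern.** Tolerance is an effect that appears and later fades. To see it within a phase, one needs at least two on-drug values in that phase, and to tell fading from ordinary development one needs a comparison group. Section 9.3 presents the extension as a second full series of three on-drug points. For the direct cognitive test, the examiner-administered standardised language test and the two lead biomarkers, the extension supplies a single point.

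What is at stake is how that point is read. If the claim stands, a month-16 value on the Mullen or on ERP habituation could be reported as evidence for or against tolerance when it cannot bear that reading. The primary endpoint and its test are not affected.

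**Working it through.** No power or alpha figure is involved. The check is a count of scheduled visits.

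**Inputs.** From Section 6.1, visits 5, 7, 8 and 9 are months 2, 4, 6 and 8. Visits 11, 12 and 14 are months 10, 12 and 16, and visit 15 is month 17. Extension time is study month minus 8, so 2, 4 and 8 extension months are study months 10, 12 and 16. Month 8 precedes extension dosing and month 17 is off drug, so neither is an on-drug extension point. Visit lists are from Sections 6.3.9, 6.3.12, 6.3.13 and 6.3.15.

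| Measure | Blinded: months 2, 4, 8 | Extension: months 10, 12, 16 |
|---|---|---|
| WCS | 3 | 3 |
| ABC-FX | 3 | 3 |
| VAS (language, behaviour) | 3 | 3 |
| CGI-I and CGI-S (language, overall) | 3 | 3 |
| Vineland-3 | 3 | 2 (12, 16) |
| MacArthur-Bates | 3 | 2 (12, 16) |
| Blood biomarkers | 2 (2, 8) | 2 (10, 16) |
| Auditory ERP | 3 | 1 (16) |
| Eye tracking | 3 | 1 (16) |
| MSEL | 2 (2, 8) | 1 (16) |
| PLS-5 | 2 (2, 8) | 1 (16) |

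**Totals over these 11 rows.** In the blinded phase 8 of 11 meet the 2/4/8 plan. In the extension 4 of 11 meet it, 3 have two points and 4 have one. Section 3 confirms that the Mullen and PLS-5 are left out at months 4 and 6.

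**By original arm, for MSEL, PLS-5, ERP and eye tracking:**

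- *Switched from placebo.* There is one on-drug value, at month 16. One value cannot show a rise followed by a fall.
- *First randomised to AFQ056.* On-drug values fall at months 2, 8 and 16 (MSEL, PLS-5) or 2, 4, 8 and 16 (ERP, eye tracking). The step from month 8 to month 16 has no concurrent placebo group and spans the return to the starting dose after month 8.

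**Shortened extensions.** For late enrollees the visit-14 battery moves to an early termination visit (Section 6.1, footnote 16). The single point then falls at a variable length of exposure. It does not exist for a child with no extension.

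**Analysis.** Section 9.6 contains no tolerance analysis. Equation 1 assumes linear change, and the extension model again targets a slope difference. A straight line cannot represent a rise and a fade. Section 9.6.3 does examine change from baseline at month 2, but not how the arm difference moves across later visits.

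**Caveat on the schedule table.** In the copy I read, Table 7's column alignment is unreliable: the last mark for these four measures, and for the WCS, sits under month 17 instead of month 16. I relied on the text of Section 6.3. Read literally, the table would leave the four measures with no on-drug extension point.

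**The case against.** The strongest reply has four parts.

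1. *The claim is hedged.* It covers most measures, not all, and is worded as an expectation. This stands in part. The hedge fits the blinded phase (8 of 11). In the extension it fits 4 of 11, although that fraction depends on whether the VAS and CGI forms are counted separately. The point does not rest on the count. The concluding sentence names cognitive and biomarker domains, and the direct cognitive test, ERP and eye tracking are among the exceptions.

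2. *The extension lengthens an existing series and need not stand alone.* This stands for children first randomised to AFQ056, who do have values in both phases. It does not help children switched from placebo, and it does not supply a control after month 8.

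3. *Long tests were omitted on purpose.* The Mullen takes 60 minutes and the PLS-5 takes 30 to 45 minutes with the child. This is a good reason for the schedule. It is also a reason to narrow the claim instead of adding visits.

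4. *Tolerance is not an objective, endpoint or hypothesis.* This is correct, and it limits the weight of the point. Tolerance is still a stated purpose of the extension.

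A reader might infer that the WCS is the only language measure with full coverage. It is not: VAS-Language and the language CGI ratings are taken at all six points. A reader might also infer that tolerance cannot be examined at all for cognition or biomarkers. The documents do not support that. ERP and eye tracking have months 2, 4 and 8 against randomised placebo, so an early effect lost by month 8 could be seen. Blood biomarkers have two on-drug extension points. The Mullen has months 2 and 8 against placebo, which is thin but usable.

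**Conclusion.** The claim in Section 9.3 is too broad for the extension. The Mullen, PLS-5, ERP and eye tracking have one of the three stated on-drug points there; Vineland-3, MacArthur-Bates and blood biomarkers have two. The Mullen, PLS-5 and blood biomarkers also miss month 4 of the blinded phase. On the four sparse measures, tolerance within the extension cannot be assessed, and neither can any tolerance in children switched from placebo. For children first given AFQ056, the month-8 to month-16 change on these measures is uncontrolled and spans the dose reset.

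This rests on the visit lists in Section 6.3 and on months 8 and 17 not being on-drug extension points. It does not extend to blinded-phase tolerance, which the schedule can address to the extent tabulated. It should be corrected, but it does not threaten the primary analysis.

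**What to change.** 1. In Section 9.3, in both the tolerance paragraph and the fifth reason for the extension, limit the within-extension claim to measures with repeated on-drug extension visits: WCS, ABC-FX, VAS and CGI, and with fewer points Vineland-3, MacArthur-Bates and blood biomarkers.

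2. In the formal statistical analysis plan, which Section 9 says is still to be developed, base the main tolerance assessment on AFQ056-placebo differences by visit in the blinded phase, with visit as a factor and an arm-by-visit term. Use every scheduled visit:
   - months 2, 4, 6 and 8 for WCS, ABC-FX, Vineland-3, MacArthur-Bates, VAS and CGI, plus months 1 and 3 for VAS and CGI;
   - months 2, 4 and 8 for ERP and eye tracking (month 4 should not be dropped, as it is the one intermediate randomised point);
   - months 2 and 8 for MSEL, PLS-5 and blood biomarkers.

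3. Report month-16 values on MSEL, PLS-5, ERP and eye tracking as descriptive only.

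The cost is wording in two places, one extra model and a narrower claim; no visit or procedure is added. The by-visit contrasts should be given as estimates with intervals, because they will be imprecise where completion is low. Section 6.3.15 expects about 50% of subjects to complete ERP and about 50% to complete eye tracking: 0.5 × 100 = 50, or about 25 per arm if split evenly. The standard error of an unadjusted difference is then √(1/25 + 1/25) = 0.28 SD, and the 95% half-width is 1.96 × 0.283 = 0.55 SD.

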## 9.4 Randomization

In order to prevent age imbalance, randomization will be stratified by age with two strata, 3-4 years and 5-6 years. Block randomization will be used with random block sizes, and age (coded as a two-level factor) will be used as a covariate in all statistical analysis. The stratification will ensure that all individuals enrolled will have a Mullen ELC (equivalent to Developmental Quotient) of <75. This will ensure sufficient symptoms to measure learning improvement and will result in enrollment of only significantly affected females, most likely excluding at least the higher functioning half of females with a full mutation (because of this, females are expected to comprise about 20% of study participants). Likewise, very high functioning males (the best functioning 10-20%) will be excluded. Thus, the males and females enrolled are expected to show heavily overlapping clinical phenotypes and developmental function and stratification is expected to be unnecessary. Further, there is no reason to expect a priori a difference in response in lower versus higher functioning individuals within the impaired group with delays enrolled, and thus even if the females are on average higher functioning within the impaired range than males, it is not clear they will respond sufficiently differently to justify stratification in a randomized design.

## 9.5 Outcomes

### 9.5.1 Primary Outcome (Including Definition)

The primary objective of this study is to demonstrate greater improvement in language in young children with FXS treated with AFQ056 in combination with an intensive standardized parent-implemented language intervention, relative to those treated with the language intervention and placebo, after 6 months of intervention, as a marker of drug effect on neural plasticity, the core problem in the disorder. This will be assessed using a primary language endpoint involving a weighted child intentional communication score coded from a 22-minute structured task which is an examiner/child dyadic play session, including a structured and unstructured play session.

Because the language intervention will specifically be targeting increased communicative behavior and increased use and production of language, the weighted communication measure

was chosen as the primary outcome because it will specifically measure child initiated communication that involves the child's use of gestures, eye contact, vocalizations, and/or words and word combinations to communicate during a standardized play session, the precise skills which are directly being taught by the language intervention. The measure is thus ideal for measuring the type of learning expected to take place from the language intervention and which potentially would be enhanced by the concomitant AFQ056 treatment. Although this measure is less well-validated than standardized language measures, it was chosen to be the primary outcome because it is so optimally matched to measure the skills the intervention is delivering and will be more sensitive to skills that are likely to improve from the language intervention than other standardized cognitive, adaptive, or language measures that have more extensive validation. Because the FXTS phenotype varies, participants will range from having minimal language/infrequent communication to using phrases or sentences and/or be more talkative. Because the WCS reflects both linguistic sophistication and frequency of communicative attempts regardless of form, it has the potential to capture change in the full range of FXTS participants. This measure will not have floor effects for non-verbal individuals seen with standardized measures. It is likely that an important effect of the interventions (both LLI and AFQ056) will be to increase social engagement and the frequency of participant communicative attempts and thus, improvement is possible even for participants who enter with sophisticated language. In addition, it is possible to extend the upper bound of the score if we find that the complexity of multiword combinations participants use changes (e.g., by adding a number rating point for communicative attempts consisting of more than three words), Thus ceiling effects are not expected.

The Weighted Communication Score coded from a standardized play session has been used in cohorts with autism spectrum disorder (ASD) and has been able to measure change in language skills with age and change in language skills in response to an intervention. Although there is not specific data on this measure in FXTS, it is not possible to validate every outcome specifically for FXTS given the rarity of the disorder. Communication and language issues are similar in FXTS and ASD so the measure is likely to perform similarly in response to an intervention in children with FXTS.

